## UNSCHEDULED FOLLOW UP VISITS

If the patient is seen by the investigator or center outside planned study follow-up, an unscheduled follow-up visits eCRF should be completed. In the case of adverse event occurrence the corresponding eCRF, documentation, and notification should be completed. In the case of a serious adverse event the corresponding eCRF and documentation should be complete in addition to notifying the Sponsor/Monitor in case the SAE is the cause of the unscheduled visit.

## PATIENT WITHDRAWAL FROM THE STUDY

A withdrawal refers to a patient who is determined to be inactive in the study due to physician discretion, patient or family choice (if the patient becomes incapacitated and is unable to continue with the study due to a family choice), and loss to follow-up or patient death. Final status shall be reported on all patients as per the informed consent. Three documented phone calls and a registered/certified letter shall be used to assure that there is minimal loss to follow-up.

In the event that patients are not reachable after repeated contact attempts, investigators must quickly clarify their whereabouts and health status with the family doctor or the contact person stated in the patient consent form (e.g., family doctor) as per the applicable regulation in each country. Patients will agree in the data exchange in the informed consent form.

If these efforts to contact the patient and his family doctor/contact person are unsuccessful, the patient shall be considered lost to follow-up. Attempts made to contact the patients and host family doctor/contact person must be recorded by the study center and monitored by the monitor.

## END OF PARTICIPATION

Subjects who have finished the required follow-up visits will be considered to have completed the study.

Withdrawal: all patients have the right to withdraw themselves from participation at any point during the study. In addition, PIs also have the authorization to terminate a patient's participation in the study. A description of the reason for the patient's termination will be documented. Reasons for termination include: completion of study, patient's voluntary withdrawal, physician-directed patient withdrawal, and death.

Upon study exit the patient will be followed per standard of care by the investigator and/or another physician.

## DURATION OF INVESTIGATION

The estimated duration for the main investigational plan (e.g. from start of screening to last participant processed and finishing the study) is approximately 36 months.

Each patient will be followed for 24 months and then exit the investigation. It is anticipated that all clinical investigation patients will be enrolled within a 24 month time period.

## VIII. SAFETY MANAGEMENT

Subjects will be carefully monitored during the study for possible Adverse Events (AEs) from the time the Subject signs the Patient Informed Consent form to the completion of their participation in the study. Any AE observed will be fully investigated by the Investigator and classified in line with the definitions of the ISO14155:2011 below.

### DEFINITIONS

#### **Adverse Event (AE):**

Any untoward medical occurrence, unintended disease or injury, or untoward clinical signs (including abnormal laboratory findings) in patients, users or other persons, whether or not related to the investigational medical device

This definition includes events related to the investigational medical device.

This definition includes events related to the procedures involved.

For users or other persons, this definition is restricted to events related to investigational medical devices.

#### **Serious Adverse Event (SAE):**

Adverse event that:

- a) led to death,
- b) led to a serious deterioration in the health of the patient, that either resulted in a life-threatening illness or injury, or a permanent impairment of a body structure or a body function, or in-patient hospitalization or prolongation of existing hospitalization, or in medical or surgical intervention to prevent life-threatening illness or injury or permanent impairment to a body structure or a body function,
- c) led to foetal distress, foetal death or a congenital abnormality or birth defect

NOTE: Planned hospitalization for a pre-existing condition, or a procedure required by the Clinical Investigation Plan, without serious deterioration in health, is not considered a serious adverse event.

#### **Device Deficiency**

Inadequacy of an investigational medical device related to its identity, quality, durability, reliability, safety or performance. This may include malfunctions, use error, or inadequacy in the information supplied by the manufacturer.

#### **Adverse Device Effect (ADE):**

Adverse event related to the use of an investigational medical device

NOTE 1: This includes any adverse event resulting from insufficiencies or inadequacies in the instructions for use, the deployment, the implantation, the installation, the operation, or any malfunction of the investigational medical device.

NOTE 2: This includes any event that is a result of a use error or intentional abnormal use of the investigational medical device.

#### **Serious Adverse Device Effect (SADE):**

Adverse device effect that has resulted in any of the consequences characteristic of a serious adverse event

## Unanticipated Serious Adverse Device Effect (USADE)

Serious adverse device effect which by its nature, incidence, severity or outcome has not been identified in the current version of the risk analysis report.

## Anticipated Serious Adverse Device Effect (ASADE)

Anticipated serious adverse device effect (ASADE) is an effect which by its nature, incidence, severity or outcome has been identified in the risk analysis report.

### EVENT SEVERITY

Event severity is classified as follows:

- **Mild:** awareness of a sign or symptom that does not interfere with the patient's usual activity or is transient, resolved without treatment and with no sequelae.
- **Moderate:** interferes with the patient's usual activity and/or requires symptomatic treatment
- **Severe:** symptom(s) causing severe discomfort and significant impact on the patient's usual activity and requires treatment.

### CAUSALITY RELATIONSHIP

The investigator will assess the causality of all adverse events in relation to the research, i.e., the relationship between the AE / SAE and the investigational treatment or any other study-related procedures.

Each SAE will be classified according to five different levels of causality:

1) **Not related:** relationship to the device or procedures can be excluded when:

- the event is not a known side effect of the product category the device belongs to or of similar devices and procedures;
- the event has no temporal relationship with the use of the investigational device or the procedures;
- the serious event does not follow a known response pattern to the medical device (if the response pattern is previously known) and is biologically implausible;
- the discontinuation of medical device application or the reduction of the level of activation/exposure - when clinically feasible – and reintroduction of its use (or increase of the level of activation/exposure), do not impact on the serious event;
- the event involves a body-site or an organ not expected to be affected by the device or procedure;
- the serious event can be attributed to another cause (e.g. an underlying or concurrent illness/ clinical condition, an effect of another device, drug, treatment or other risk factors);
- harms to the patient are not clearly due to use error;
- In order to establish the non-relatedness, not all the criteria listed above might be met at the same time, depending on the type of device/procedures and the serious event.

2) **Unlikely:** the relationship with the use of the device seems not relevant and/or the event can be reasonably explained by another cause, but additional information may be obtained.

3) **Possible** the relationship with the use of the investigational device is weak but cannot be ruled out completely. Alternative causes are also possible (e.g. an underlying or concurrent

illness/ clinical condition or/and an effect of another device, drug or treatment). Cases where relatedness cannot be assessed or no information has been obtained should also be classified as possible.

4) **Probable** the relationship with the use of the investigational device seems relevant and/or the event cannot reasonably be explained by another cause, but additional information may be obtained.

5) **Causal relationship**: the serious event is associated with the investigational device or with procedures beyond reasonable doubt when:

- the event is a known side effect of the product category the device belongs to or of similar devices and procedures;
- the event has a temporal relationship with investigational device use/application or procedures;
- the event involves a body-site or organ that
- the investigational device or procedures are applied to;
- the investigational device or procedures have an effect on;
- the serious event follows a known response pattern to the medical device (if the response pattern is previously known)
- the discontinuation of medical device application (or reduction of the level of activation/exposure) and reintroduction of its use (or increase of the level of activation/exposure), impact on the serious event (when clinically feasible);
- other possible causes (e.g. an underlying or concurrent illness/ clinical condition or/and an effect of another device, drug or treatment) have been adequately ruled out;
- harm to the patient is due to error in use;
- In order to establish the relatedness, not all the criteria listed above might be met at the same time, depending on the type of device/procedures and the serious event.

## INVESTIGATOR REPORTING RESPONSIBILITIES

### Notification of events to the sponsor

The investigator should report to the sponsor the following events, whether expected or not, in the corresponding sheet of the eCRF, with the exception of AEs / SAEs detected before the patient has signed the patient consent form.

- AE
- SAE
- Device Deficiencies that did not but might have led to a SAE if:
  - i. Suitable action had not been taken or
  - ii. Intervention had not been made or
  - iii. If circumstances had been less fortunate
- New findings/updated in relation to already reported events

If an AE / SAE is present at the beginning of study prior to the patient providing signed consent to participate in the study, only its worsening should be reported.

The investigator shall notify the sponsor immediately and not later than 24 hours after the investigator has become aware of a SAE or device deficiency that might have led to a SAE. The investigator must ensure that all additional relevant information that becomes available is also forwarded to the sponsor immediately after the initial notification.

The investigator shall transmit to the sponsor all relevant supporting documents related to the SAE (i.e., copy of laboratory exams, hospitalization reports indicating the SAE) ensuring anonymization of the documents and indicating the identification number of the patient in the study.

### **How to report**

The investigator will report “to the sponsor, without unjustified delay, all serious adverse events and device deficiencies that could have led to a serious adverse device effect; this information shall be promptly followed by detailed written reports” [ISO 14155:2011 § 9.8 b]. Device malfunctions and use errors should also be reported without unjustified delay.

All Serious Adverse Events (SA(D)Es), including all device deficiencies should be reported to the Sponsor within 24 hours of awareness of an event via the Adverse Event electronic Case Report Form in the study’s electronic database, as that will trigger an immediate e-notification to the Sponsor and MedPass. Additional information can be provided to the Sponsor or MedPass via email, telephone, or fax using the information below.

#### **Monitor:**

MedPass International  
[name]  
[name]  
[contact]  
[contact]  
[[contact]](mailto:[contact])

The investigator will document all AEs on the Adverse Event Form, including (at a minimum) a description of the event, date of onset, severity, relationship to the investigational device and/or procedure, required interventions, duration, and outcome. The investigator will monitor all AEs until they are resolved, determined to be a chronic condition or the patient is lost to follow-up. The investigator will report all AEs regardless of whether it is anticipated or unanticipated and regardless of classification, seriousness, intensity, outcome or causality.

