#### FOLLOW-UP PROCEDURES/ASSESSMENTS

**Post-procedure management:** Standard hospital protocols for the management of patients after mitral valve surgery shall be followed. Unless other indications for anticoagulation are present, all patients shall receive only 325 mg/day low dose aspirin, beginning on arrival to the intensive care unit).

**Discharge:** All patients shall be discharged from the hospital at the discretion of the attending cardiac surgeon.

For the patients where a procedure was finally not started (i.e. echo results) or started but finally interrupted with no use of the study device, the discharge date will be registered as the study termination date and no more data will be collected for these patients.

For the patients where a procedure attempt has been made, Harpoon device used, but procedure was finally not completed and patients were converted to another treatment a safety period of 30 days post procedure will be required. Clinical data will be collected and CRF completed until that date. The 30 days Follow up date will be registered as the study termination date for these patients.

For the patients successfully treated, the expected follow period is 24 months. Patients will be followed until that date except under certain circumstances (withdrawal, death, lost to follow up).

Prior to dismissal all patients shall undergo a comprehensive pre-dismissal TTE, as well as a physical assessment (vide supra) in accordance with the schedule of Clinical Investigations.

**Patient follow-up:** The expected follow up period after the Harpoon procedure is from 24 months. Assessments will be completed at 30days, Discharge, 6 months, 12 months and 24 months.

30 days follow up (+10/0 days post procedure) - Patients will be seen in the outpatient clinic and the following exams will be performed:

- Physical exam, including NHYA evaluation if needed
- ECG
- TTE AE evaluation
- Concomitant medication changes

6 months follow up (+/- 30 days) - Patients will be seen in the outpatient clinic and the following exams will be performed:

- Physical exam, including NHYA evaluation if needed
- TTE
- AE evaluation
- Concomitant medication changes

12 months follow up (+/- 30 days) - Patients will be seen in the outpatient clinic and the following exams will be performed:

- Physical exam, including NHYA evaluation if needed
- 6 minute walk test (6MWT)
- SF36 questionnaire
- TTE
- AE evaluation
- Concomitant medication changes

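### The AE follow-up rule conflicts with the early-exit rules: events open at exit may go unrecorded, and SAEs from discharge to day 30 are not collected in patients without device use

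*Combined protocol and SAP*

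**What the plan says.** Two sets of rules in the combined protocol and SAP bear on how long an adverse event is followed.

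**Follow-up of events.** In Section VIII, the text after the monitor's contact block under How to report says that "The investigator will monitor all AEs until they are resolved, determined to be a chronic condition or the patient is lost to follow-up". It makes "relationship to the investigational device and/or procedure, required interventions, duration, and outcome" part of the minimum content of the AE form. Under Notification of events to the sponsor, the list of what must be reported includes "New findings/updated in relation to already reported events".

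**Exit from the study.** Section VII, Follow-up Procedures/Assessments, sets three exit points.
- The procedure was never started, or was "started but finally interrupted with no use of the study device". In both of these cases the section directs that "the discharge date will be registered as the study termination date and no more data will be collected for these patients".
- The device was used but the procedure was not completed, and "patients were converted to another treatment a safety period of 30 days post procedure will be required". For this group, "Clinical data will be collected and CRF completed until that date", and the 30-day visit is the termination date.
- Successfully treated patients are followed for 24 months.

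The opening of Section VIII limits AE monitoring to the period from consent "to the completion of their participation in the study". Section VII, Enrollment, likewise registers events only until the patient leaves the study. End of Participation then passes the patient to standard of care.

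**The concern.** The first set of rules ends follow-up when the event ends. The second ends it when the patient exits. Study exit is not among the end points in the AE rule, and nothing exempts open events from the exit rules. A site with an open event at early exit has to break one instruction or the other, and different staff may choose differently.

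Two things are at stake. One is the duration and outcome of events open at exit, which the AE form requires. The other is the primary safety endpoint, freedom from SAEs during the procedure, at discharge and at 30 days. If data stop at discharge, a patient whose operation was begun and abandoned never reaches the 30-day assessment. Yet that patient was enrolled at consent, and Section X says that all data are captured by intent to treat.

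**Working it through.** The plan has no figure to reproduce here: Section X states that no formal sample size was calculated. The check is a comparison of text, with a little arithmetic for scale.

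**1. The exit rules set against the AE rule**

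| Patient group | Data stop at | SAEs to day 30 collected? | Course of an AE open at exit collected? |
|---|---|---|---|
| Not started, or interrupted without device use | Discharge | Only to discharge | No, under the follow-up section; yes, under the AE rule |
| Device used, converted | 30-day visit | Yes | Same conflict, but only after that visit |
| Successfully treated | 24 months | Yes | Same question at 24 months, from the Enrollment section and the opening of Section VIII |

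The 30-day visit window is +10/-0 days, so it cannot fall before day 30. In converted patients the 30-day SAE count is therefore intact.

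**2. Does any text reconcile the rules?** Early termination might be thought to count as loss to follow-up, which would end the AE rule's duty. It does not. Patient Withdrawal from the Study reserves that status for patients who cannot be reached after documented attempts. No section says which rule prevails or how an AE ongoing at exit is to be recorded.

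**3. Does a no-device patient have operative exposure?** If the procedure was never started, no. If it was started, yes. Treatment Procedure/Assessments describes general anesthesia, heparin, thoracotomy, opening of the pericardium and a purse-string suture before the introducer is in place. The AE definition includes events related to the procedures involved. The gap between discharge and day 30 therefore matters mainly for operations started and then interrupted.

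**4. Scale**
- Weight of one patient: with the maximum of 20 enrolled, and this patient counted in the denominator, 1/20 = 5 percentage points. Section X does not define the denominator, so this is an assumption.
- Frequency of early exit: the documents give none. For an assumed rate p of early exit of any kind, the expected number is 20p and the chance of at least one is 1 - (1 - p)^20.
  - p = 2%: 0.4 expected; chance 33%.
  - p = 5%: 1.0 expected; chance 64%.
  - p = 10%: 2.0 expected; chance 88%.
- The earlier feasibility study reports procedural success in 13 of 13. The upper limit of the two-sided 95% interval for non-success is 1 - 0.025^(1/13) = 24.7%, or 20 x 0.247 = 4.9 patients of 20. That record does not rule out early exits.

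Interruption without device use is only part of early exit, and harm to the data also needs an event that is open at discharge or arises after it. The chances above therefore overstate how often data would be missing at each assumed p.

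**The case against.** The best defense is that the sections do different jobs. The exit rules end scheduled CRF collection, the Enrollment section and the opening of Section VIII set the window for registering new events, and the AE rule says how long a registered event is followed. The duty to report updates supports this, and How to report lets further information reach the sponsor or monitor by email, telephone or fax. This stands in part. A reader might infer that outcomes of open events are certainly lost, but the documents do not say that the exit rules override the AE rule, so the supportable statement is that these outcomes may not be recorded. The defense fails for the discharge group, where the wording of the data stop is absolute.

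A reader might also infer that the 30-day endpoint is compromised in converted patients. It is not: their data run through the 30-day visit.

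A third inference would size the problem from the two reoperations for delayed tamponade in the earlier study, on days 5 and 13 (2/13 = 15%). The documents do not support this. All 13 patients had procedural success with cords implanted, and under this plan such patients would be followed for 24 months. The device also includes the valved introducer (Device Description), so a no-device patient has not had it placed in the ventricle. A rate from implanted patients cannot be carried over.

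Finally, the group is small, of unknown size, and includes patients who had no operation. That is correct and limits the weight of the point.

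**Conclusion.** The conflict is in the current text, and it holds within limits. For an AE open at early exit the site cannot satisfy both rules, and its later course and outcome may not be recorded. The primary 30-day SAE endpoint is affected only in the no-device group, mainly where the operation was started and then interrupted. There, a worsening or a new SAE between discharge and day 30 would not be collected. In converted patients only the course after the 30-day visit is at risk.

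The likely number of patients is unknown. One event is worth 5 percentage points if 20 patients are enrolled and the patient is in the denominator; both are assumptions. The point merits a change because the correction is cheap and affects an endpoint that the plan calls primary, not because a large bias has been shown.

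**What to change.** Reconcile four places: Enrollment and Follow-up Procedures/Assessments in Section VII, and the opening and the AE documentation paragraph of Section VIII. State in each, or once with cross-references, that:

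- (a) any AE ongoing at the study termination date, whatever the reason for termination, is updated in the eCRF until it has resolved, is judged chronic, the patient is lost to follow-up, or consent is withdrawn; any worsening to serious is reported as an SAE with its date;
- (b) for patients whose procedure was started but interrupted without device use, SAE status is recorded to day 30. This replaces the stop on all further data for that group.

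Part (b) is needed as well as (a), because following only events already open would still miss a new SAE after discharge. Part (a) also settles the same question at the 24-month exit.

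The cost is a few sentences of protocol text and a follow-up contact for the few patients who exit early. Treatment and scheduled procedures do not change.
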